3.2.3 Statistical Analysis

3.2.3.1 Data Description and Comparison between Groups

Measurement data (such as age, AFP level, liver function indicators, etc.): Normally distributed data are expressed as mean \pm standard deviation, and independent sample t - test (for two groups) or analysis of variance (for multiple groups) is used for comparison between groups; non - normally distributed data are expressed as median (interquartile range), and Mann - Whitney U test (for two groups) or Kruskal - Wallis test (for multiple groups) is used.

Count data (such as immunotherapy response type, typing results, etc.): Expressed as frequency (percentage), and chi - square test is used for comparison between groups; if the frequency of a cell < 5 , Fisher's exact probability method is used instead.

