3.1.1 Inclusion Criteria

- ① ≥ 18 years old.
- ② Patients who are treated in multiple centers including Sir Run Run Shaw Hospital, Zhejiang University School of Medicine (the leading unit) and diagnosed with primary hepatocellular carcinoma by surgical pathological histology.
- ③ They have received targeted drug combined with immune checkpoint inhibitor treatment after the specimen collection time point (post - surgery or post - puncture) (that is: local treatments such as TACE, ablation, etc. are allowed before the start of targeted - immunotherapy combination treatment, but an interval of ≥ 4 weeks from the targeted - immunotherapy treatment is required).
- ④ Have measurable tumor lesions at the observation start point (according to RECIST 1.1 criteria), and can judge the tumor response status (including complete response CR, partial response PR, stable disease SD, or progressive disease PD) through imaging examination during the observation (such as post - treatment evaluation).
- ⑤ Have accessible frozen tumor tissue samples from surgical resection (sample volume $\geq 3g$); or tumor tissue samples obtained by puncture (puncture samples need to meet the pathological diagnosis requirements, and the sample quality can support subsequent transcriptome sequencing and analysis).
- ⑥ Voluntarily participate in this study and sign the informed consent form. If the subject

is unable to read and sign the informed consent form due to incapacity and other reasons, their guardian shall act as the agent for the informed process and sign the informed consent form. If the subject is unable to read the informed consent form (such as illiterate subjects), a witness shall witness the informed process and sign the informed consent form.

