3.2.2 Immunotherapy Response Evaluation System

3.2.2.1 Primary Observation Indicators

(1) Time to Progression (TTP)

Definition: The time from the start of targeted - immunotherapy combination treatment to

the first time meeting the mRECIST progression criteria.

Evaluation Criteria:

Target lesions: The sum of the diameters of arterial - phase enhancement increases by $\geq 20\%$ compared to the baseline and the absolute value $\geq 5\text{mm}$;

Non - target lesions: New lesions appear or existing non - target lesions have definite progression;

Distant metastasis: New occurrences of lung, bone, or lymph node metastases.

(2) Objective Response Rate (ORR)

Definition: The proportion of patients achieving complete response (CR, disappearance of arterial - phase enhancement in all target lesions) and partial response (PR, the sum of the diameters of target lesions is reduced by $\geq 30\%$).

Evaluation Time: For each line of targeted - immunotherapy combination treatment regimen received by the patient, the determination is made simultaneously at Week 8, Week 16, Week 24 of the regimen treatment, and at disease progression (or regimen termination). If the patient changes the targeted - immunotherapy treatment regimen due to poor efficacy, the treatment cycle of the new regimen needs to be recorded separately (Weeks 8, 16, 24 are recalculated from the start time of the new regimen), and the CR/PR status is evaluated at the corresponding time points. In the final ORR calculation, the CR/PR status achieved by the patient in a certain regimen only corresponds to the treatment cycle and evaluation time of that regimen, that is, it is clearly associated with the efficacy data of the specific targeted - immunotherapy combination regimen (including the first regimen or the subsequent new regimens).

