3.2.3.3 Immunotherapy Response Analysis

The differences between groups in objective response rate (ORR) and disease control rate (DCR) are verified by chi - square test or Fisher's exact probability method, and the efficacy judgment follows the mRECIST criteria.

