3.2.4 Protection Measures for Vulnerable Groups

The vulnerable groups that may be involved in this study include the mentally ill/cognitively impaired/critically ill patients/elderly/illiterate, etc. This study will take the following measures to protect their interests: 1) Ensure that the subjects are fully informed. If the subject is unable to read and sign the informed consent form due to

incapacity, their guardian shall act as the agent for the informed process and sign the informed consent form. If the subject is unable to read the informed consent form (such as illiterate subjects), a witness shall witness the informed process and sign the informed consent form. 2) If it is a critically ill patient, the researcher will closely monitor the vital signs of such subjects, and report in a timely manner once there is a situation.

IV. Sample Size Calculation

This study plans to include subjects from 10 top - three hospitals nationwide. Calculate the new typing score of HCC for each sample through the 29 - gene signature. It is estimated that there will be 100 cases in the new typing cohort and 250 cases in other typing cohorts.

Therefore, the final planned total sample size of this study is 350 cases.

V. Data Management and Confidentiality

All records related to the subject's identity will be kept confidential, and these materials will not be disclosed outside the scope permitted by relevant laws and/or regulations.

VI. Informed Consent

For the prospective observational study part involved in this study, before the subjects are included in this study, the researcher responsible for the informed consent discussion should introduce the purpose, nature, procedure, and possible benefits and risks of this study to them in written form completely and comprehensively. The subjects should be informed that they have the right to withdraw from the study at any time. Before inclusion, each subject should be fully informed and have sufficient time to consider whether to participate. Only after the subject voluntarily participates and signs the informed consent form can they be included in this study.

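### Response type (CR, PR, SD, PD) is ordered, but section 3.2.3.1 compares it between subtypes with a chi-square test that ignores the order (low severity)

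*Protocol*

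**What the plan says.** Protocol section 3.2.3.1 sets one rule for all count data and gives response type as its first example: "Count data (such as immunotherapy response type, typing results, etc.): Expressed as frequency (percentage), and chi - square test is used" for comparison between groups. It continues: "if the frequency of a cell < 5 , Fisher's exact probability method is used instead". No trend or rank test is named for ordered categories. The Mann-Whitney test appears in the same section, but only for non-normal measurement data.

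The response levels are listed in section 3.1.1, item 4: "including complete response CR, partial response PR, stable disease SD, or progressive disease PD".

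The formal response endpoints are handled elsewhere. ORR is a primary indicator in section 3.2.2.1, defined as "The proportion of patients achieving complete response (CR, disappearance of arterial - phase enhancement in all target lesions) and partial response". Section 3.2.3.3 covers its test: "The differences between groups in objective response rate (ORR) and disease control rate (DCR) are verified by chi - square test or Fisher's exact probability method".

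On group sizes, section IV (Sample Size Calculation) says: "It is estimated that there will be 100 cases in the new typing cohort and 250 cases in other typing cohorts". It gives no response rates, effect size or power. Section 3.2.3.4 sets the significance level at 0.05 without saying whether tests are one- or two-sided.

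**The concern.** The four response levels run from best to worst, and section II sets out to confirm that the new subtype responds better. The Pearson chi-square on a 2 x 4 table gives the same P value if the four columns are put in any other order. It therefore tests whether the two distributions differ in any way, and spreads its power over patterns that have nothing to do with better response. A rank or trend test puts one degree of freedom on the question asked.

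This is a method that the protocol states, so it is not a matter of detail left to a later analysis plan. What is at stake is the efficiency and the interpretation of a supportive comparison. The validity of the test and the primary ORR analysis are not at stake.

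**Working it through.** **Plan's own figure.** 100 + 250 = 350, as stated in section IV. Nothing further can be reproduced, because no response rates or power are given.

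**Inputs.** n1 = 100 (new subtype) and n2 = 250 (others, pooled), from section IV. Alpha is 0.05 from section 3.2.3.4, taken as two-sided (assumption). CR/PR/SD/PD percentages are assumptions throughout.

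**One case by formula.** New subtype 5/35/35/25%, others 3/25/37/35%.

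- Differences d: 0.02, 0.10, -0.02, -0.10.
- Pooled proportions p = (100 x new + 250 x others)/350: 0.0357, 0.2786, 0.3643, 0.3214.
- Multiplier n1 x n2/N = 25,000/350 = 71.43.
- Chi-square noncentrality = 71.43 x sum(d²/p) = 71.43 x (0.0112 + 0.0359 + 0.0011 + 0.0311) = 5.67. On 3 df (critical value 7.81) the power is about 49%.
- Wilcoxon: mean relative ranks r = 0.0179, 0.1750, 0.4964, 0.8393; sum(d x r) = -0.0760; variance of r = 0.0747. Noncentrality = 71.43 x 0.0760²/0.0747 = 5.52. On 1 df the power is about 65%.

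Nearly all of the signal (5.52 of 5.67) lies in the ordered direction. The chi-square test spends three degrees of freedom to detect it.

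**Simulation at 100 versus 250**

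| New subtype, % | Others, % | Chi-square, 3 df | Wilcoxon | Gap |
|---|---|---|---|---|
| 5/35/35/25 | 3/25/37/35 | 50% | 66% | 16 |
| 6/36/34/24 | 3/27/37/33 | 53% | 65% | 12 |
| 8/37/33/22 | 4/26/37/33 | 69% | 81% | 12 |
| odds ratio 1.5 | 5/25/40/30 | 33% | 46% | 13 |
| odds ratio 1.8 | 5/25/40/30 | 62% | 77% | 15 |
| odds ratio 2.0 | 5/25/40/30 | 77% | 89% | 12 |

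The odds-ratio rows apply a common odds ratio to the others' distribution. Two further baselines (3/17/45/35% and 10/25/40/25%) give gaps of 11 to 15 points. Both tests reject at close to 5% when there is no difference.

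**Non-monotone case.** With 12/20/28/40% against 5/25/40/30%, there is more CR but also more PD in the new subtype. The chi-square test then has about 79% power and the Wilcoxon test about 10%.

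**Against the planned ORR test.** In the first three rows, the 2 x 2 test of CR + PR has about 59%, 57% and 76% power. In the same run the Wilcoxon test has 65%, 63% and 81%, a gain of about 5 to 7 points.

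**Limit of the simulation.** The chi-square column is the Pearson test without the switch to Fisher's test. In the first row a cell count below 5 occurs in about 52% of tables, so the switch would often apply if the count meant is the observed one. Fisher's test on a 2 x 4 table has no ordering either, so the criticism carries over, but the exact gap under the full rule was not computed.

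**The case against.** The strongest reply is that this rule carries none of the study's inference. ORR and DCR are binary, and a chi-square or Fisher test suits them. Response type is only an example of count data in a general section, item 4 of section 3.1.1 is an eligibility condition, and response type could even mean responder versus non-responder, in which case the table is 2 x 2 and the point falls away. An unordered test on ordered categories is also valid, and it is the better one when the difference is not monotone. Most of this stands and is why the severity is low. It does not remove the point: section 3.2.3.3 already deals with ORR and DCR separately, the only response levels listed are the four, and the rule names response type expressly.

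A reader might infer three stronger things.

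- **That the primary ORR analysis is weakened.** It is not; its test is unaffected.
- **That an ordinal test costs nothing.** It does cost power against a non-monotone difference, as the 10% against 79% example shows, although that pattern is not the stated hypothesis.
- **That the switch to Fisher's test uses observed counts and so loses power.** The text says only the frequency of a cell, without observed or expected. Exact enumeration of 2 x 2 tables at 100 versus 250 shows the switch almost idle when ORR is 10% or more in both groups and the new subtype does at least as well: a cell below 5 has probability 2.4% at 10% versus 10%. At low rates in the hypothesised direction, switching on observed counts has slightly more power than switching on expected counts (others 2%, new 8%: 71.9% against 69.8%). It loses 2 to 3 points only where the new subtype does worse at low rates (new 3%, others 10%: 60.9% against 64.0%). A single table can flip, such as 4/100 versus 27/250: smallest expected count 31 x 100/350 = 8.9, chi-square P = 0.043, Fisher P = 0.059. But that table runs against the hypothesis, and with Yates' correction the chi-square P is 0.070. What remains is an ambiguous wording.

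**Conclusion.** The point holds for the four-level comparison. The test named in section 3.2.3.1 ignores the order of CR, PR, SD and PD, and at 100 versus 250 it has about 11 to 16 points less power than a tie-corrected Wilcoxon test against a consistent shift towards better response. That size rests on assumed response distributions, two-sided testing at 0.05, pooling of the other subtypes, and a monotone difference. Severity is low: the four-level response is not a named endpoint, and the gain over the ORR test already planned is only about 5 to 7 points. For the Fisher switch, only the missing word *expected* is at issue.

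**What to change.** In section 3.2.3.1, take response type out of the chi-square examples. State that the four-level response is compared between the new subtype and all others by the tie-corrected Wilcoxon rank-sum test (a permutation version if the table is sparse), with a proportional-odds odds ratio and 95% confidence interval. Show the full frequency table beside it, so that a non-monotone pattern can be seen. Keep the two-group tests for ORR and DCR in section 3.2.3.3 as they are. In the Fisher rule, refer to an expected cell frequency below 5.

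The cost is two sentences. No further data or patients are needed, and the rank test is already named in the section for other variables. The price is lower power against a non-monotone difference.

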3.2.3.2 Survival Analysis

Use the Kaplan - Meier method to draw survival curves of time to progression (TTP) and post - progression survival (PPS), and compare the survival differences between the new typing cohort and other typing cohorts through Log - rank test; use the Cox proportional hazards regression model to analyze the impact of 29 - gene set typing and clinical factors (such as Child - Pugh class, changes in tumor markers) on the progression risk.

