these subtypes to the TCGA HCC cluster respectively, and screen out the subtypes that cannot be completely matched as new subtypes; further analyze the differential genes between the new subtypes and other subtypes. The screening criteria are: the ratio of gene expression between the new subtype and other subtypes > 4 , the false discovery rate (FDR) < 0.01 , and the gene expression in the new subtype > 1 and < 1 in other subtypes. Through this method, this study finally obtained a set of differential genes containing 29 genes.

Based on this, this study plans to use this 29 - gene set as a standard, obtain frozen surgical tissues from liver cancer patients for transcriptome sequencing, type the patients, and compare the differences in immunotherapy response between the new subtype and other subtypes at the large - sample level, aiming to provide a basis for precise immunotherapy of liver cancer.

II. Research Objectives

Evaluate the differences in immunotherapy response (including indicators such as objective response rate, disease control rate, and progression - free survival) between the new subtype defined by the 29 - gene set system and other subtypes, and confirm that patients with the new subtype have a higher response rate to immunotherapy.

III. Research Design and Methods

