3.2.1.2 Clinical Data Integration

Structured extraction of subjects' baseline data (age, gender, Child - Pugh class, etc.), treatment information (targeted - immunotherapy combination regimen, dosage, and cycle, etc.), imaging evaluation (enhanced CT/MRI reports, etc.), and survival status (last follow - up date or death time, etc.) from the electronic medical record system. Simultaneously collect AFP (electrochemiluminescence method), PIVKA - II (enzyme - linked immunosorbent assay), and liver function biochemical data (total bilirubin, albumin, INR, etc.). The detection frequency matches the imaging evaluation cycle (that is, equivalent to clinical routine).

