3.2.2.2 Secondary Observation Indicators

(1) Core Indicators of Immunotherapy Response

① Progression - Free Survival (PFS)

Definition: The time from the start of targeted - immunotherapy combination treatment to the first disease progression (determined according to mRECIST) or death from any cause, whichever occurs first.

Evaluation Method: Combine imaging examinations (once every 8 weeks) and survival status follow - up, and use the Kaplan - Meier method to perform Log - rank test to compare the differences between groups.

② Overall Survival (OS)

Definition: The time from the start of targeted - immunotherapy combination treatment to the patient's death from any cause; for lost - to - follow - up patients, the last follow - up date is used as the censored data.

Evaluation Method: Record the survival status through regular telephone/outpatient follow - up, draw survival curves, and analyze the differences between groups.

Dynamic changes of tumor markers.

(2) Dynamic Monitoring Related to Tumors

Dynamic changes of tumor markers

Monitoring Indicators: Alpha - fetoprotein (AFP), protein induced by vitamin K absence or antagonist - II (PIVKA - II), detected once at baseline and every 4 weeks.

Judgment Criteria: An increase of $\geq 20\%$ compared to the baseline and lasting for more than 4 weeks, combined with imaging results to assist in predicting the progression

risk (such as the early warning value of marker increase before imaging progression).

(3) Evaluation of Treatment - Related Status

① Correlation with Liver Function Status

Evaluation Nodes: Collect liver function data (Child - Pugh class, total bilirubin, albumin, INR) simultaneously when disease progresses.

Analysis Logic: Compare with baseline liver function, exclude interfering factors such as drug - induced liver injury, and evaluate the direct impact of tumor progression on liver function injury.

② Survival Analysis after Progression

Record Content: Treatment adjustment plans after disease progression (changing targeted drugs, adding local treatments, etc.).

Analysis Indicators: Post - progression survival (PPS, the time from disease progression to death or the end of the study), and analyze the impact on survival by combining differences in treatment plans.

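### The Cox regression in 3.2.3.2 lists on-treatment marker change beside 29-gene typing; in a joint fit, the subtype hazard ratio would not be the total subtype difference in progression

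*Protocol*

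**What the plan says.** All references are to the Protocol.

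- **Model (3.2.3.2).** Cox regression is to assess the influence of 29-gene typing and of "clinical factors (such as Child - Pugh class, changes in tumor markers) on the progression risk". Cox regression is mentioned nowhere else. The same section compares TTP between subtypes by an unadjusted log-rank test.
- **Time zero (3.2.2.1, and PFS in 3.2.2.2).** TTP is "The time from the start of targeted - immunotherapy combination treatment to" first progression, and PFS has the same starting point.
- **Marker timing (3.2.2.2, item 2).** AFP and PIVKA-II are "detected once at baseline and every 4 weeks". The criterion is a rise of at least 20% "compared to the baseline and lasting for more than 4 weeks".
- **Purpose of the markers (same item).** They help to predict progression, for example through "the early warning value of marker increase before imaging progression".
- **Child-Pugh class.** Section 3.2.1.2 lists it under "baseline data (age, gender, Child - Pugh class, etc". Section 3.2.2.2 collects it again at progression. Section 3.2.3.2 gives it no time point.
- **Objective (II).** The study is to evaluate how the new subtype differs from the others in ORR, DCR and PFS, and to "confirm that patients with the new subtype have a higher response rate to immunotherapy".

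**The concern.** Subtype is fixed by the tumour sample, before treatment starts. Marker change happens during treatment, and the Protocol itself treats it as a forerunner of the outcome. It may therefore lie on the path from subtype to progression. Holding such a variable constant removes whatever part of the subtype effect passes through it, and the remaining coefficient does not answer the stated objective.

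This matters because subtype is not randomised and patients come from 10 hospitals. The log-rank, chi-square and Fisher tests adjust for nothing. The Cox regression is the only covariate-adjusted analysis of the subtype comparison and the only planned source of a hazard ratio. Yet the one marker covariate it names arises after time zero, while the baseline marker values, which are collected, are not named. A reader of the published model could take its subtype HR as the subtype effect on progression.

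**Working it through.** **1. The Protocol's own figures.** The only relevant figure is the sample size, 100 + 250 = 350, which is correct as a sum. No HR, event count, marker effect or subtype-marker association is given. Every HR below rests on assumed inputs.

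**2. When marker change can be known.** The marker baseline is taken to be the start of treatment; this is inferred, not stated. With tests every 4 weeks, the first post-baseline value is at week 4. A sustained rise can then be confirmed at week 4 + 4 = 8 at the earliest, or at week 12 if *more than 4 weeks* is read strictly. Scans are every 8 weeks, so the first is at week 8. The criterion cannot be known at time zero, and some patients will have progressed before it can be met.

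**3. Effect of conditioning, simplest case.** Suppose a rise is known at the outset, occurs in a proportion p1 of the new subtype and p0 of the others, and multiplies the hazard by m. Let d be the subtype HR among patients with the same marker status. The subtype HR at time zero, ignoring the marker, is

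d × (1 − p1 + p1·m) / (1 − p0 + p0·m).

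A joint model returns about d. Simulated Cox fits (100 versus 250 patients, 12 months, 1000 trials each) are set beside the formula:

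| d | p1 vs p0 | m | Formula | Simulated, subtype only | Simulated, joint |
|---|---|---|---|---|---|
| 0.7 | 30% vs 50% | 2 | 0.7 × 1.3/1.5 = 0.61 | 0.61 | 0.69 |
| 0.7 | 20% vs 60% | 2 | 0.7 × 1.2/1.6 = 0.53 | 0.54 | 0.70 |
| 1.0 | 20% vs 60% | 3 | 1.0 × 1.4/2.2 = 0.64 | 0.67 | 1.00 |
| 0.7 | 40% vs 40% | 2 | 0.7 × 1.4/1.4 = 0.70 | 0.72 | 0.70 |

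The simulated subtype-only values lie slightly nearer 1 because high-risk patients leave the risk set early. In the first row, the share of trials with P < 0.05 for subtype falls from 88% to 65%. In the last row subtype and marker are unrelated, and almost nothing changes.

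**4. Effect of coding.** Step 3 treats the marker as known at the outset, which the criterion in 3.2.2.2 does not allow. Simulations of a sustained rise that occurs during treatment and is less frequent in the new subtype gave these subtype HRs:

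| Subtype only | With time-dependent rise | With fixed ever/never rise |
|---|---|---|
| 0.82 | 0.91 | 0.78 |
| 0.56 | 0.62 | 0.54 |
| 0.64 | 0.70 | 0.57 |
| 0.85 | 0.94 | 0.72 |
| 0.55 | 0.66 | 0.38 |

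The first two rows assume that no rise starts after week 24. The last three come from a separate set (8-weekly scans, 4-weekly tests, 30% vs 50% or 20% vs 60% with a rise by week 24, rise HR 2 to 3). Shifts of that size under fixed coding arise when new rises continue after week 24. Time-dependent coding moves the subtype HR toward 1. Fixed coding leaves it about where it was or moves it away from 1.

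**5. The marker's own HR under fixed coding.** A patient must stay progression-free long enough to be recorded as having a sustained rise, so this coding uses future information. With a true marker HR of 1.0 and a rise unrelated to subtype, fixed coding gave 0.48 to 0.76 when rises start only by week 24, and 0.18 to 0.43 when they keep starting. Time-dependent coding gave 0.98 to 1.03.

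**The case against.** The strongest reply is that 3.2.3.2 names a method and gives an illustrative list of factors. It fixes neither a covariate set, nor the coding, nor the number of models, and an SAP commonly settles these. No objective is tied to the Cox coefficient: ORR and DCR are tested by chi-square or Fisher, and TTP and PFS by log-rank. The sentence can also be read as a model of prognostic factors for progression, where marker change may well belong.

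Much of this stands. Joint fitting is not stated, so the point is conditional on it. A prediction model may include marker change, but its subtype coefficient is still not the subtype effect. What does not stand is that this is merely an unstated detail: the Protocol itself names a post-treatment factor beside typing in its only covariate-adjusted analysis.

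Three stronger readings are tempting, and the document supports none of them.

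- *The subtype effect will be diluted.* The direction depends on the subtype-marker link and on the coding, and the Protocol gives neither.
- *The primary comparisons are biased.* The log-rank and response tests do not condition on markers.
- *Fixed ever/never coding spoils only the marker HR.* That holds only if marker rise is unrelated to subtype. With a link, the subtype HR can move too, as step 4 shows.

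**Conclusion.** The point holds in conditional form. If typing and marker change are fitted jointly, the subtype HR is not the total subtype difference in progression. When the new subtype lowers the markers, the HR moves toward 1 with time-dependent coding, and is unchanged or moves away from 1 with fixed ever/never coding. Fixed coding also biases the marker's own HR downward.

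The size cannot be fixed from the document. The HRs above show that the shift can be negligible or large; they do not predict this study's result. The problem is confined to the interpretation of the regression. It deserves correction because that regression is the only adjusted analysis of a non-randomised comparison.

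**What to change.** In 3.2.3.2:

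- Estimate the subtype HR for progression with pre-treatment covariates only: baseline AFP, baseline PIVKA-II and baseline Child-Pugh class. Remove marker change from this model and write *baseline* before Child-Pugh.
- Analyse marker change in a separate model for its early-warning value, either as a time-dependent covariate or from a landmark. State that the subtype coefficient in that model is not the subtype effect.

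**Cost.** The change needs new wording, one extra model, dated marker results and simple handling of missing baseline markers. The baseline values are already collected. A landmark drops early progressors: at week 16, with exponential TTP and an assumed median of 22 to 39 weeks, 1 − 2^(−16/22) = 40% down to 1 − 2^(−16/39) = 25% of patients. Time-dependent coding avoids this loss.

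**A separate matter.** Section 3.2.1.2 ties marker tests to the imaging cycle, which 3.2.2.2 sets at 8 weeks, whereas 3.2.2.2 schedules markers every 4 weeks. The two passages should be reconciled, because the frequency decides when a sustained rise can be confirmed. The point above does not depend on it.

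### Tumour-marker change, known only during follow-up, is listed as a Cox factor with no timing rule; fitted as a fixed covariate, its hazard ratio would be biased toward protection

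*Protocol*

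**What the plan says.** Section 3.2.3.2 uses a Cox proportional hazards model to study how the 29-gene typing and "clinical factors (such as Child - Pugh class, changes in tumor markers) on the progression risk" matter. Child-Pugh class is among the items that section 3.2.1.2 lists as baseline data.

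The clock is set in section 3.2.2.1, where TTP is "The time from the start of targeted - immunotherapy combination treatment to" the first progression by mRECIST. PFS in section 3.2.2.2 has the same origin.

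Section 3.2.2.2 judges a marker rise as an increase of at least 20% "compared to the baseline and lasting for more than 4 weeks". AFP and PIVKA-II are "detected once at baseline and every 4 weeks". The rise is meant, together with imaging, to help predict progression, "such as the early warning value of marker increase before imaging progression". Progression itself is read from "imaging examinations (once every 8 weeks").

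Section 3.2.1.2 gives another marker schedule: "The detection frequency matches the imaging evaluation cycle (that is, equivalent to clinical routine").

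No time-dependent covariate, landmark or joint model appears anywhere in the protocol. Nor does it say that the marker factor is fixed.

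**The concern.** A covariate in an ordinary Cox model is treated as known from time zero. A sustained marker rise is not. To be classed as a riser, a patient must stay progression-free and under observation until the rise is confirmed. Those who progress early fall into the non-riser group, or have no value at all.

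With fixed coding, a riser therefore sits in the riser group at every event time before confirmation without being able to have the event. That pulls the marker's HR down whatever its true effect. Fitting the marker in a model of its own does not help if the coding is the same.

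At stake is the reading of a named secondary indicator. A marker with no effect, or one that moderately raises the risk of progression, could be reported as protective, and a strong warning marker as weak.

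**Working it through.** **Figures in the plan.** The protocol gives no figure for the marker analysis, so there is none to reproduce. Its only design figure is the sample size, 100 + 250 = 350.

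**Step 1: earliest possible confirmation, from the protocol's own schedules.**
- Four-weekly sampling (3.2.2.2): samples at weeks 0, 4, 8, 12. A rise first seen at week 4 has lasted 8 − 4 = 4 weeks at week 8, which is not more than 4. At week 12 it has lasted 12 − 4 = 8 weeks. Earliest confirmation is week 12, or week 8 if exactly 4 weeks counts.
- Sampling on the imaging cycle (3.2.1.2, taken as 8-weekly): samples at weeks 0, 8, 16. A rise first seen at week 8 is confirmed at week 16.
- First scan: week 8.

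On the strict reading, a patient who progresses at the first scan can never be a riser, under either schedule.

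**Step 2: how many patients that is.** The protocol gives no median TTP. I assume exponential TTP with medians of 26, 39 and 52 weeks. The share progressing by week 8 is 1 − 2^(−8/median):
- median 26: 1 − 2^(−8/26) = 0.192, or 67 of 350
- median 39: 1 − 2^(−8/39) = 0.133, or 46 of 350
- median 52: 1 − 2^(−8/52) = 0.101, or 35 of 350

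So 10% to 19% of the cohort would be non-risers by construction at the first scan alone.

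**Step 3: size of the bias, by simulation.** From the protocol: 350 patients, 8-weekly scans, 4-weekly markers, and confirmation at the first sample more than 4 weeks after the rise is seen (8 weeks later). Assumed: median TTP 26, 39 or 52 weeks; median time to rise 16, 26 or 52 weeks; all or half of patients able to rise; censoring uniform over weeks 52–104. There were 100 runs per setting. Ranges are across settings.

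| True HR of rise | Fixed 'ever rose' HR | Runs with fixed HR below 1 | Time-dependent HR |
|---|---|---|---|
| 1 | 0.19–0.52 | 100% | 0.97–1.03 |
| 1.5 | 0.27–0.72 | 100% | 1.26–1.45 |
| 2 | 0.32–0.87 | 89–100% | 1.46–1.85 |
| 3 | 0.42–1.12 | mixed (14–100% at median TTP 52) | 1.74–2.52 |
| 5 | 0.55–1.38 | mixed | – |
| 8 | 0.64–1.53 | mixed | – |

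One strong-effect setting (true HR 5, median TTP 52, median time to rise 26, half able to rise) gives 1.32 with fixed coding against 3.43 with time-dependent coding. There the direction is right and the size far too small. A week-16 landmark gives 0.94–1.04 for a neutral rise and 1.22–1.74 for a true HR of 2.

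A narrower set of assumptions gives the same pattern: confirmation one 4-week visit later, median TTP 24 or 32 weeks, 20–40% with a rise starting within 24 weeks, and 72 weeks of follow-up. Fixed coding gives 0.31–0.40 for a true HR of 1 and 0.48–0.63 for a true HR of 2. Time-dependent coding gives 0.99–1.00 and 1.85–1.90.

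**Step 4: the rise as a herald of progression.** Here coming progression triggers the rise in 40% or 70% of patients, with a mean lead of 8 or 16 weeks (200 runs per setting).
- No unrelated rises: fixed coding 1.05–2.28, time-dependent 3.23–8.73. The average direction is right, with heavy attenuation.
- Unrelated background rises added (median 104 weeks): fixed coding 0.67–1.08, time-dependent 1.85–3.73. In ten of the twelve settings at least 78% of runs fell below 1.

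**The case against.** The strongest objection is that the protocol never says the factor is fixed. It calls the indicator dynamic, and the R survival package named in section 3.2.3.4 can fit time-varying data. Coding in time is often left to the SAP, which may exist unseen. **This stands in part.** A reader might infer from the listing beside Child-Pugh class that the protocol prescribes a fixed covariate, but it does not, so the point must be conditional. It is still more than missing detail: the protocol itself chose a post-baseline state for a model timed from treatment start, and listed it with a baseline factor without any rule for its timing.

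A second objection is that a reader might conclude the marker will look protective and the early-warning answer will have the wrong sign. **This stands.** Reversal is nearly certain only for true HRs up to about 2. From about 3 upward, or when the rise mainly heralds progression, the fixed-coding HR can stay above 1. What holds throughout is downward bias.

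Third, section 3.2.3.2 does not cite the 20% criterion, so the change could be coded in other ways. **This also stands in part.** A change measured at a fixed visit or a time-updated value would behave differently. An unconfirmed rise coded as fixed gave 0.24–0.67 when neutral but up to 4.44 as a herald of progression. The result depends on a coding left open, which is a reason to state it.

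Last, nothing says that this Cox model is the early-warning analysis, and the objective in section II does not mention markers. **This limits the weight of the point:** the figures above concern the marker's own HR, not a primary result.

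**Conclusion.** The concern holds in conditional form. Section 3.2.3.2 places a state that arises only during follow-up in a Cox model timed from treatment start, with no rule for its timing. If it is fitted as a fixed 'ever rose' covariate, its HR is biased toward protection. Neutral and moderate effects (true HR up to about 2) nearly always appear protective. Strong or heralding effects are attenuated and may or may not reverse.

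The mechanism and the week-12 (or week-8, or week-16) confirmation dates follow from the protocol's own schedules. The sizes rest on assumed TTP, rise rates and censoring. The documents do not support the stronger claims that fixed coding is prescribed or that the sign is bound to be wrong. The point is worth correcting before the data are seen.

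**What to change.** In section 3.2.3.2, state that marker rise is analysed as a time-dependent covariate that switches on at the date the section 3.2.2.2 criterion is confirmed, using start-stop data in the R survival package. Alternatively, specify a landmark analysis among patients still progression-free at a pre-specified scan. State that the rise is not entered as a fixed factor from treatment start. Whether the marker belongs in the same model as the subtype is a separate question, which this change does not decide.

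Reconcile the marker schedules in 3.2.1.2 (imaging cycle) and 3.2.2.2 (every 4 weeks), and say whether exactly 4 weeks counts, so that the confirmation date is well defined.

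The cost is a sentence or two, slightly longer code and no new data. Time-dependent coding leaves some attenuation from the confirmation delay (1.46–1.85 for a true HR of 2). A landmark loses the patients who progress before it. At week 16, with a neutral rise and the medians assumed above, that is 1 − 2^(−16/52) = 19% to 1 − 2^(−16/26) = 35% of the cohort.
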